
Correlative / Exploratory studies
	
Patients will have a bone marrow aspirate and biopsy performed on screening, within the loading phase (day -7) at least 2 hours after the selinexor administration, and at the time of disease progression. The bone marrow biopsies will be used to construct a tumor microarray for the analyses below. Bone marrow aspirates will be aliquoted and a portion will be CD138 selected. If a patient has <5% involvement plasma cells in the bone marrow in screening, a repeat bone marrow biopsy is not needed on day -7 (loading).
 
Myeloma Patient Bone Marrow Biopsy Microarrays  Plasma cells in tumor microarrays (produced from patient bone marrow biopsies) will be identified by lambda or kappa light-chain staining and examined for the expression and intracellular location (nucleus versus cytoplasm) of topoisomerase II<math>\alpha</math>, topoisomerase II<math>\beta</math>, p53, XPO1, I<math>\kappa</math>B, NF-<math>\kappa</math>B, and possibly other biomarker of relevance before and after in vivo treatment with selinexor and at the time of disease progression.
 
Myeloma Patient Bone Marrow Aspirates  Patient bone marrow aspirates collected during screening will be used to evaluate the predictive value of baseline ex vivo sensitivity testing with selinexor and LD. The lymphocyte fraction of patient bone marrow aspirates will be isolated by ficoll-gradient centrifugation and incubated overnight in the presence of selinexor (0, 0.156, 0.625, 2.5, 10 and 40 <math>\mu</math>M), +/- doxorubicin (2<math>\mu</math>M), and if adequate sample is available, KPT8602 (0, 0.156, 0.625, 2.5, 10 and 40 <math>\mu</math>M) +/- dexamethasone (10<math>\mu</math>M) . . Ex vivo sensitivity to will be assayed in CD-138/light chain double positive myeloma

cells by flow cytometry and activated caspase 3 apoptosis assay for EC50 analysis.

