	
(HBV surface antigen)
 
 
9. Any underlying condition that would significantly interfere with the absorption of an oral medication
 
10. Grade >2 peripheral neuropathy at baseline (within 14 days prior to loading phase (day -7))
 
11. Serious psychiatric or medical conditions that could interfere with treatment
 
12. Participation in an investigational anti-cancer study within 3 weeks prior to loading phase (day -7)
 
13. Concurrent therapy with approved or investigational anticancer therapeutic. Patients are allowed to receive corticosteroids for the treatment of non-malignant disorders in doses not to exceed the equivalent of prednisone 20 mg/day
 
14. Patients with coagulation problems and active bleeding in the last month (peptic ulcer, epistaxis, spontaneous bleeding)
 
15. Patients who have had a previous allogeneic transplant for treatment of multiple myeloma within the past 6 months or have evidence of clinically significant GVHD
 

Screening Assessments
	
Signed written informed consent
 
Demographics and medical history (prior therapy)
 
Pregnancy test (if applicable) (within a week of loading phase)
 
Physical examination and vital signs (within 2 weeks of loading phase)
 
Ophthalmologic exam (within 4 weeks of loading phase)
 
Cardiac evaluation: echocardiogram or MUGA (within 6 weeks of loading phase), ECG
 
Hematology (CBC) (within 2 weeks of loading phase)
 
Clinical chemistry (with LDH, b2microglobulin,) (within 2 weeks of loading phase)
 
Urinalysis (within 4 weeks of loading phase)
 
Coagulation (within 2 weeks of loading phase)
 
Assessment of disease status (within 4 weeks of loading phase) (SPEP, 24h UPEP, serum free light chain)
 
Bone marrow aspiration and biopsy with cytogenetics, FISH, MyPRS (gene expression profile) and correlative endpoints described above (within 4 weeks of loading phase)
 
Chest radiograph (within 4 weeks of loading phase)
 
Skeletal survey (within 4 weeks of loading phase)
 
Concomitant medication

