
Treatment and Post-Treatment Assessments
	
Loading Phase  Physical examination and vital signs (includes weight and ECOG performance status) (on day -7 only)  Hematology (on day -7 only)  Clinical chemistry (on day -7 only)  Assessment of disease status (Day -7) (SPEP, 24h UPEP, serum free light chain)  PK of selinexor (appendix C)  Adverse events and concomitant medication  Pregnancy test (if applicable)  Bone Marrow aspiration and biopsy at least 2 hours post selinexor dosing on day -7
 
Cycle 1  Physical examination and vital signs (includes weight and ECOG performance status)  Hematology  Complete clinical chemistry (weekly in cycle 1)  Assessment of disease status (SPEP, 24h UPEP, serum free light chain)  PK of doxorubicin, and selinexor and PD (appendix C)  Adverse events and concomitant medication  Pregnancy test (if applicable)
 
Cycle 2 and Beyond  Physical examination and vital signs (on day 1) (includes weight and ECOG performance status)  Cardiac evaluation (echocardiogram or MUGA every 2 cycles if patient has prior anthracycline exposure with greater than 450 mg/m^2)  Hematology (on day 1)  Complete clinical chemistry (on day 1)  Assessment of disease status (SPEP, 24h UPEP, serum free light chain) (on day 1)  Adverse events and concomitant medication  Pregnancy test (if applicable)  PK of doxorubicin, and elinexor and PD (appendix C)
 
Final Visit (end of study)  Physical examination and vital signs (includes weight and ECOG performance status)  Pregnancy test (if applicable)  Cardiac evaluation (echocardiogram or MUGA)  Hematology

--	--

	
Complete clinical chemistry
 
Assessment of disease status (SPEP, 24h UPEP, serum free light chain)
 
Bone marrow aspiration and biopsy (in the event of discontinuation due to disease progression)
 
Adverse events and concomitant medication
 
Pregnancy test (if applicable)

Response	
Response will be assessed per the uniform response criteria of the IMWG incorporating minimal response (<math>\geq 25\%</math> decrease in serum M protein and <math>\geq 50\%</math> decrease in the 24h urine m spike).

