 Hematology: hemoglobin, white blood cell (WBC) count, absolute neutrophil counts and platelets. During loading, a hematology sample is obtained on day -7. During cycles 2-8 and maintenance, hematology sample is obtained on day 1 of the cycle only.

 Serum Chemistry: Sodium, Potassium, Chloride, Bicarbonate, BUN, Creatinine, and Glucose, Calcium, ALT, AST, Alkaline Phosphatase, Total Bilirubin, LDH, Total Protein, Albumin. During screening only, this will also include amylase, lipase, uric acid, TSH and creatine kinase. During loading, a chemistry sample is obtained on day -7. During cycles 2-8 and maintenance, chemistry sample is obtained on day 1 of the cycle only.

 Coagulation test include prothrombin time (PT), international normalization ratio (INR), and activated partial thromboplastin time (aPTT)

 A bone marrow aspirate and biopsy will be performed at baseline, on day-7 (at least 2 hours after selinexor administration) and at the end of treatment in case of progressive disease. The screening bone marrow will include standard cytogenetics, FISH and gene expression profiling by MyPRS. In addition, bone marrow biopsy and aspirate on screening and day-7 will be used for PD markers. Finally, CD138 positive cells from the screening bone marrow aspirate and the end of treatment bone marrow aspirate will be frozen in pellets for future molecular characterization by next generation sequencing. If a patient has <5% involvement plasma cells in the bone marrow in screening, a repeat bone marrow biopsy is not needed on day -7 (loading).

 Disease status will be measured by assessment of myeloma paraprotein and measurement of plasmacytomas (if applicable). Specifically patients will have a serum protein electrophoresis, 24h urine for protein electrophoresis and serum free light chain assay during screening, start of the loading phase, on day 1 of every cycle. In addition, patients will have a skeletal survey at baseline, and at progression. Finally, patients with

plasmacytomas should have measurement of their plasmacytomas at baseline, and every 2 cycles using a modality at the discretion of the treating physician.

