### **11.6 Analysis of the Phase II**

For the primary endpoint in Phase II trial, we are interested in comparing the overall response rate of this combination with historical efficacy data using liposomal doxorubicin and dexamethasone in patients with relapsed and refractory myeloma. The overall response rate and its 95% confidence will be calculated using the method proposed by Atkinson and Brown[49]. This confidence interval takes into account the nature of the two-stage Simon design.

The secondary endpoints include progression-free survival (PFS), overall survival (OS), safety, and duration of response. Patients will be followed for survival and progression until termination of the study. PFS is defined as the time from start of treatment to death of any cause, disease progression, or the date of last follow-up, whichever comes first. OS is defined as the time from start of treatment to death of any cause or the date of last follow-up, whichever comes first. The time-to-event data will be estimated using the Kaplan-Meier method. The median of PFS and OS and 95% confidence intervals will be computed. The effect on time-to-event data adjusting for other factors (such as age and tumor stage) will be analyzed using the Cox proportional hazards regression models.

As the exploratory endpoints, the association between the change of each biomarker (e.g., nucleus to cytoplasm ratio, p53, CRM1, I $\kappa$ B and NF $\kappa$ B) from screening to day 1 of cycle 1 and the response to the therapy will be examined by the Satterthwaite t-test or the Wilcoxon rank sum test. The appropriate transformation such as log-transformation may be considered if necessary. In addition, we will examine if the disease progression is associated with the change from screening to date of progression or from day 1 of cycle 1 to date of progression. No multiplicity adjustment is planned due to the nature of exploratory study. A two-sided p-value of < 0.05 will be considered significant. We expect that 12 or more of 29 patients in Phase II are responders. With a two-sided significance level of 5%, 29 samples will provide 80.4% power to detect an effect size (mean difference divided by standard deviation) of 1.2 when the numbers of responders and non-responders are 12 and 17, respectively.

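### Section 11.6 uses cycle 1 day 1 as the on-treatment biomarker time point, but no marrow is scheduled then; the scheduled on-treatment marrow is on day -7

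*Combined protocol and SAP*

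**What the plan says.** **The analysis.** Section 11.6 states that the association between each biomarker's change "from screening to day 1 of cycle 1 and the response to the therapy will be examined by the Satterthwaite t-test", with a rank-sum test as the alternative. For progression, it says that "we will examine if the disease progression is associated with the change from screening to date of progression". The second option that it gives there is worded "or from day 1 of cycle 1 to date of progression". The example markers are the nucleus to cytoplasm ratio, p53, CRM1, IkB and NFkB. Significance is two-sided at 0.05 without adjustment for multiplicity. The power given is 80.4% for an effect size of 1.2 with 29 samples, split into 12 responders and 17 non-responders.

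**The marrow schedule.** The Synopsis (Correlative / Exploratory studies) has a "bone marrow aspirate and biopsy performed on screening, within the loading phase (day -7) at least 2 hours after the selinexor administration", with a further one at progression. The biopsy microarrays are read before and after in vivo "treatment with selinexor and at the time of disease progression". The Synopsis list of loading-phase assessments has "Bone Marrow aspiration and biopsy at least 2 hours post selinexor dosing on day -7". Footnote 13 of the study calendar reads "A bone marrow aspirate and biopsy will be performed at baseline, on day-7 (at least 2 hours after selinexor administration", adds a marrow at end of treatment in case of progressive disease, and assigns the screening and day -7 marrow to the pharmacodynamic markers. The Synopsis and footnote 13 both waive the day -7 biopsy when screening plasma cells are below 5%.

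**The blood schedule.** Appendix C draws leukocytes (XPO1 inhibition) and cytokines on day -7, on days 1, 8 and 15 of cycle 1, and on cycle 2 day 1.

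**The concern.** A change score needs a sample at each end. Two of the three change scores named in Section 11.6 start or end on a day when no marrow is taken, yet the markers listed there are localization markers, which the Synopsis and Section 10.1 measure on marrow biopsies and aspirates.

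What is at stake is the planned clinical check of the trial's mechanism. The rationale in Section 1.5.1 is that blocking XPO1 keeps topoisomerase II alpha and p53 in the nucleus and restores sensitivity to doxorubicin. The biomarker-response comparison examines this in patients and has its own power statement. Taken literally, it has no marrow data. Taken as a comparison with day -7, it may have fewer pairs than the power statement assumes.

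**Working it through.** **1. Marrow time points, side by side**

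| Place | Screening | Day -7 / loading | Cycle 1 day 1 | Progression / end of treatment |
|---|---|---|---|---|
| Synopsis, correlative studies | yes | yes, at least 2 h after selinexor | no | yes |
| Synopsis, treatment assessments | – | yes, at least 2 h after selinexor | no | yes, if progressive disease |
| Section 5 calendar row | yes | yes | blank | yes |
| Footnote 13 | yes | yes, at least 2 h after selinexor | no | yes, if progressive disease |
| Section 6.2.2 (treatment phase only) | – | yes, loading phase, at least 2 h after selinexor | no | – |
| Section 10.1, biopsies | yes | yes | no | yes, at relapse |

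The Synopsis screening list, Section 6.2.1 and Section 6.2.3 cover only screening or end of treatment, so they could not show a cycle 1 day 1 marrow and are not counted as evidence.

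**2. Change scores in Section 11.6 against that schedule (marrow markers)**

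- Screening to cycle 1 day 1, against response: no second sample, so 0 scheduled pairs.
- Cycle 1 day 1 to progression: no first sample, so 0 scheduled pairs.
- Screening to progression: both samples are scheduled, in patients who progress.

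**3. Could Section 11.6 mean blood?** Appendix C has 16 draws on 5 visit days. Leukocytes are taken at 3 (day -7) + 3 (cycle 1 day 1) + 2 (day 8) + 2 (day 15) + 2 (cycle 2 day 1) = 12 of them. Cytokines are taken pre-dose on each of the 5 visit days. Neither is drawn at screening or at progression. Blood therefore supplies neither cycle 1 day 1 variable as worded. The earliest blood baseline is day -7 pre-dose.

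**4. Are day -7 and cycle 1 day 1 interchangeable?** No. The loading phase lasts one week, 168 h. Section 1.3 gives a selinexor half-life of 6 to 7 h, so the interval is 168/7 = 24 to 168/6 = 28 half-lives. The day -7 sample reflects acute exposure to one dose. Section 11.6 does not say whether its cycle 1 day 1 value is before or after dosing.

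**5. The stated power.** For a two-group t-test, df = n1 + n2 − 2 and the noncentrality is d × √(n1·n2/(n1+n2)).

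- n = 12 and 17, d = 1.2: 1.2 × √(204/29) = 3.18, df = 27, power 86.6%. A simulated Satterthwaite test gives 86.2%.
- Wilcoxon test at its minimum asymptotic relative efficiency of 0.864: effective sizes 12 × 0.864 = 10.4 and 17 × 0.864 = 14.7, power 80.9%. Rounded to 10 and 15: 1.2 × √(150/25) = 2.94, df = 23, power 80.4%.

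The stated 80.4% matches the conservative Wilcoxon calculation with 29 complete observations.

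**6. Effect of the day -7 waiver.** The documents do not say how many patients will have screening plasma cells below 5%. The shares below are assumptions, applied equally to responders and non-responders.

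| Assumed share without a pair | Pairs | t-test | Wilcoxon, minimum efficiency |
|---|---|---|---|
| 0% | 12 + 17 = 29 | 86.6% | 80.9% |
| 10% | 11 + 15 = 26 | 82.6% | 76.3% |
| 20% | 10 + 14 = 24 | 79.1% | 72.4% |
| 30% | 8 + 12 = 20 | 70.1% | 62.9% |

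**The case against.** The strongest reply is that this is a label error with an obvious reading. There is only one on-treatment marrow before progression, footnote 13 already ties the screening and day -7 marrow to the pharmacodynamic markers, and the Synopsis frames the comparison as before and after selinexor. That stands. A reader might infer that an analyst would be free to pick a substitute visit after seeing the data. The documents do not support this, since there is no second on-treatment marrow to choose.

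A reader might also infer that the progression analysis is lost. It is not. Section 11.6 joins its two progression variables with an *or*, and the screening-to-progression variable has scheduled samples. That this change exists only in patients who progress follows from its definition and is not a separate fault.

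Third, Section 11.6 never uses the word marrow, its marker list is open, and Section 10.1 names leukocyte XPO1 and cytokines as possible response biomarkers. This is fair for those blood markers, but they lack the screening and progression samples that the wording requires. It does not help the localization markers, which are not measured in the scheduled blood.

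Finally, the analyses are exploratory. That stands and sets the size of the point.

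**Conclusion.** The conflict is real and minor. As worded, the biomarker-response analysis has no scheduled pair for the marrow localization markers, and only one of the two progression variables can be computed for them. Section 11.6 needs to be reconciled with the sampling schedule.

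The stated 80.4% power is not a miscalculation, but it applies only if all 29 patients have both samples. Under the assumed shares of 10% to 30% without a pair, it falls to between 76.3% and 62.9% on the conservative Wilcoxon basis. The true share is unknown.

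A reader should not infer that the trial's main conclusions are affected. The Simon two-stage rule uses response counts only, and neither the primary nor the secondary endpoints use a biomarker.

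The conclusion rests on the text, the calendar and Appendix C. The correlative flowchart in Section 10.1 could not be read, but the text around it places no marrow on cycle 1 day 1.

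**What to change.** In Section 11.6:

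- For the marrow markers, replace cycle 1 day 1 with day -7 (post-selinexor) in both places, matching footnote 13.
- Name the specimen. Either specify the paired biopsy microarray, or reconcile Section 10.1, which lists aspirates only at screening and relapse, with footnote 13, which also lists a day -7 aspirate.
- Define the analysis set as patients with both samples. State that it may be smaller than 29 because of the plasma-cell waiver, and that the 80.4% power holds only with 29 pairs.
- If leukocyte XPO1 mRNA or cytokines are intended, list them separately with day -7 pre-dose as baseline, and do not give them a change to progression, since no such draw exists.

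The cost is a few lines in Section 11.6 and, if the aspirate is used, one line in Section 10.1. No sample, visit or patient is added.

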### 6.2.3 End of Treatment

Patients who discontinue therapy for any reason must have an end of treatment (EOT) visit completed 30 days (± 7 days) after the last application of study drug.

At the EOT visit, the patients will undergo the following assessments:

Pregnancy test (if applicable)	A serum pregnancy test will be performed in pre-menopausal women and women who are post-menopausal for < 2 years to exclude that a pregnancy occurred under treatment
Physical examination and vital signs	
 
• Body weight
 
• Blood pressure, pulse, temperature
 
• Physical examination
 

Cardiac evaluation	12-lead ECG, echocardiogram or MUGA
Hematology	Hemoglobin, white blood cell (WBC) count, absolute neutrophil count and platelet count
Clinical chemistry	Sodium, potassium, chloride, bicarbonate, BUN, creatinine, glucose, calcium, phosphate, magnesium, ALT, AST, alkaline phosphatase, total bilirubin, total protein, albumin, LDH
Assessment of disease status	The disease status will be assessed by serum protein electrophoresis, 24h urine for protein electrophoresis and serum free light chain assay
Adverse events and concomitant medication	Assessed on an ongoing basis
Bone Marrow biopsy and Aspirate	A bone marrow aspiration and biopsy will be obtained at the end of treatment and before the initiation of another therapy in patients with progressive disease

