## 10 CORRELATIVE STUDIES AND PHARMACOKINETICS

### 10.1 Exploratory Correlative Studies (See Correlative Flowchart below)

**Bone Marrow Aspirates Summary:** Bone Marrow aspirates will be collected from patients at the time of screening and at relapse. Mononuclear cells isolated from patient aspirates will be assayed for drug sensitivity (EC50). A portion of these aspirates will be aliquoted, CD138 selected and stored for subsequent molecular characterization by next generation sequencing. A portion of the lymphocyte fraction will be incubated overnight in the presence of selinexor (100nm & 300nM) and cytospin slides made to assay the intracellular location (nucleus versus cytoplasm) of topoisomerase II $\alpha$ , p53, XPO1, Ikb $\alpha$ , histone control, and possibly other biomarkers of relevance with and without treatment with selinexor.

**Myeloma Patient Bone Marrow Biopsy Microarrays Summary:** The bone marrow biopsies collected at screening, day-7 and at relapse will be used to construct a tumor microarray for biomarker analysis. Plasma cells in tumor microarrays will be identified by lambda or kappa light-chain staining and examined for the expression and intracellular location (nucleus versus cytoplasm) of topoisomerase II $\alpha$ , p53, XPO1, Ikb $\alpha$ , histone control, and possibly other biomarkers of relevance before and after *in vivo* treatment with selinexor.

**Myeloma Patient Bone Marrow Aspirates at Screening:** Patient bone marrow aspirates collected during screening will be used to evaluate the predictive value of baseline *ex vivo* sensitivity with selinexor +/- doxorubicin and if adequate sample is available selinexor +/- dexamethasone and KPT-8602 +/- dexamethasone. The lymphocyte fraction of patient bone marrow aspirates will be isolated by ficoll-gradient centrifugation and incubated overnight in the presence of selinexor (0, 0.156, 0.625, 2.5, 10, 40  $\mu$ M) +/- doxorubicin (2  $\mu$ M), and if adequate sample available selinexor (0, 0.156, 0.625, 2.5, 10, 40  $\mu$ M) +/- dexamethasone and (10  $\mu$ M). KPT-8602 (0, 0.156, 0.625, 2.5, 10, 40  $\mu$ M) +/- dexamethasone (10  $\mu$ M). *Ex vivo* sensitivity will be assayed in CD-138/light chain double positive myeloma cells by flow cytometry and activated caspase 3 apoptosis assay for EC50 analysis. Assay order of importance based on cell numbers will be selinexor, selinexor+dexamethasone, selinexor+doxorubicin, KPT-8602 and KPT-8602+dexamethasone.

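### Section 11.6 relates progression to a marrow change that is measured only in patients who progress, so the association cannot be estimated

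*Combined protocol and SAP*

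**What the plan says.** The exploratory paragraph of Section 11.6 has two parts. The first relates response to "the change of each biomarker (e.g., nucleus to cytoplasm ratio, p53, CRM1" and others) from screening to cycle 1 day 1, using a Satterthwaite t-test or a Wilcoxon rank sum test. The second part adds that "we will examine if the disease progression is associated with the change from screening to date of progression". As an alternative, it lets the interval begin at cycle 1 day 1 instead, with the same end point. No test or model is named for this second part. Two-sided p below 0.05 is to be called significant, without multiplicity adjustment.

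The sampling is set elsewhere:

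- Section 10.1: "The bone marrow biopsies collected at screening, day-7 and at relapse will be used to construct a tumor microarray for biomarker analysis".
- Section 5, footnote 13: the late marrow is taken "at the end of treatment in case of progressive disease".
- Section 6.2.3: it is "obtained at the end of treatment and before the initiation of another therapy in patients with progressive disease".
- The synopsis (correlative studies and final visit) also ties the late marrow to progression.

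**The concern.** The outcome is progression and the explanatory variable is a change that ends at progression. The later of the two samples is collected only because the outcome has occurred, so the outcome decides who has a predictor value. An association needs the outcome to vary among patients in whom the predictor is measured, and here it does not.

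The stated question then has no answer in the data. The analysis would have to be dropped, or a before-and-after change in progressors would be reported as an association with progression. The second is a real risk, because the sentence names no method and any p below 0.05 in this paragraph counts as significant. Patients also have an invasive procedure at progression partly for this purpose, so the sample deserves an analysis that it can support.

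**Working it through.** **1. The plan's own figure.** The only number given for the biomarker analyses is 80.4% power for a standardised difference of 1.2, with 12 responders and 17 non-responders at two-sided 5%. A noncentral t calculation gives 86.6%. Multiplying the group sizes by 0.864, the minimum asymptotic relative efficiency of the Wilcoxon test, gives 12 × 0.864 = 10.4 and 17 × 0.864 = 14.7. Rounded to 10 and 15, the power is 80.4%, which reproduces the plan. That figure concerns response; none is given for the progression analysis.

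**2. Who has a marrow, and when.**

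| Time | Progressors | Non-progressors | Source |
|---|---|---|---|
| Screening | yes | yes | Section 5, footnote 13 |
| Day -7, after selinexor | yes, unless under 5% plasma cells at screening | same rule | Section 5, footnote 13 |
| Cycle 1 day 1 | none scheduled | none scheduled | Section 5 calendar |
| End of treatment | yes | none scheduled | footnote 13; Section 6.2.3; synopsis |

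The calendar's cross for marrow at the final visit looks unconditional, but the row carries footnote 13, which limits it to progressive disease.

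**3. Could blood supply the late value?** No. Appendix C ends pharmacodynamic blood sampling at cycle 2 day 1, with no draw at progression or end of treatment.

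**4. The count.** Let m of the 29 phase II patients progress.

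- Progressors with a change to progression: at most m.
- Non-progressors with that change: 0 of 29 − m.

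For example, with an assumed m = 20, there are up to 20 values among progressors and 0 among the 9 others.

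- A two-group difference has variance σ²(1/n₁ + 1/n₂), which is undefined at n₂ = 0.
- In a logistic model every usable record has outcome 1, so the slope is not identified.
- A hazard ratio for progression in the trial population cannot be obtained either, because patients without the event have no covariate value.

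None of this depends on m. The date that ends the interval also does not exist for a non-progressor.

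**5. What the samples do support.** A paired change among progressors can be estimated. For a paired t-test at two-sided 5%, the standardised change d detectable with 80% power solves

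1 − F(t₀.₉₇₅,ₘ₋₁; m − 1, d√m) = 0.80,

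where F is the noncentral t distribution function. The plan does not state the number of progression marrows, so m is assumed:

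| m | Detectable d |
|---|---|
| 15 | 0.78 |
| 20 | 0.66 |
| 25 | 0.58 |
| 29 | 0.54 |

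This tests whether a marker has changed by the time of progression, not whether the change is associated with progressing.

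**The case against.** The strongest reply is that the sentence was meant as a within-patient comparison. The synopsis describes the markers as examined before treatment, after treatment and at progression, which is a longitudinal description, and both intervals end at a date that only progressors have. The two-group tests belong to the response sentence, so an empty comparison group is not strictly something the plan prescribes. It is right that no test is assigned to the progression question. But the sentence asks about association with progression, and that wording does not describe a paired change. If a paired change was intended, the sentence should say so, which is the first half of the fix.

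Change could also be related to time to progression among progressors only. That can be computed, but it conditions on the outcome, uses a value measured at the event itself, and is not specified.

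Some non-progressors may have a marrow to establish complete remission under Appendix A. Such samples are not in the calendar, not assigned to these assays and not time-matched.

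Two points stand. The analysis is exploratory, so the response rate, the two-stage rule, PFS, OS and safety are unaffected. A Cox model on the early change answers a new question, namely whether an early drug effect predicts PFS, and the exemption for patients with under 5% plasma cells must be declared.

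**Conclusion.** The concern holds; the sentence is wrong as written. From scheduled samples, the number of non-progressors with the required change is 0 for any number of events, so progression against no progression cannot be related to it. This rests on two readings: that the markers named in Section 11.6 are the marrow markers of Section 10.1, and that the late marrow is limited to progressive disease, on which footnote 13, Section 6.2.3 and the synopsis agree. Exploratory status limits the consequence but does not make the analysis possible. The sentence should be corrected before analysis.

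**What to change.** Replace the progression sentence in Section 11.6 with two analyses.

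1. **Change at progression.** In patients with a progression marrow, compare each biomarker at progression with screening, and separately with the day -7 marrow, by the Wilcoxon signed-rank test. Report the number of pairs and the median change with its interval. Call the result change at progression, not association with progression.
2. **Early change and PFS.** Fit a Cox model of PFS on the screening to day -7 change, one biomarker at a time. These samples are scheduled before outcome is known. State that patients with under 5% marrow plasma cells at screening are exempt from the day -7 marrow, and report how many are left out for this reason. Label the question as whether early change predicts PFS.

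Drop cycle 1 day 1 as a starting point for this analysis, since no marrow is scheduled then, and name the day -7 marrow instead.

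The cost is a change of wording. No new samples or assays are needed, and Section 11.6 already uses Cox regression. Keeping the question as now worded would instead require a time-matched marrow in patients who have not progressed, which means additional invasive sampling.
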